# **Exploratory Analyses:**

To study the efficacy of CBD on the aspects of PD listed in Section IV, 1.4 and plasma levels of cytokine in PD.

**Exploratory Outcome Measures:** The efficacy of CBD on these aspects of PD are measured by the same standardized tools used for safety and tolerability (listed in Section IV, 1.4). The effect of CBD is also measured by Clinical Global Impression (CGI) and Patient Global Impression-improvement (PGI-I) and Change (PGI-C). CGI is a three-item observer-rated scale that measures illness severity (CGIS), global improvement or change (CGIC) and therapeutic response. The CGI is rated on a seven-point scale, with the severity of illness scale using a range of responses from 1 (normal) through to 7 (amongst the more severely ill patients). CGI-C scores range from 1 (very much improved) through to 7 (very much worse). Treatment response ratings should take account of both therapeutic efficacy and treatment-related adverse events and range from 0 (marked improvement and no side-effects) and 4 (unchanged or worse and side-effects outweigh the therapeutic effects). Each component of the CGI is rated separately. PGI-I is a global index that may be used to rate the response of a condition to a therapy (transition scale). It is a simple, direct, easy to use scale that is intuitively understandable to patients. PGI-C is rated on a seven-point scale, evaluating all aspects of patient' health and determining if there has been an improvement or not. The change from baseline to the end of 2.5 mg/kg/day is compared between the two groups.

Change of plasma levels of cytokine from baseline to the end of 2.5 mg/kg/day will be compared between the two groups.

Assessments	Primary	Secondary	Exploratory
	(efficacy)	(safety +tolerability)	(efficacy)
MDS UPDRS Part III motor score	Х		
MoCA		X	Х
Detailed cognitive battery		X	Х
Anxiety short form		X	Х
NPI		X	Х
SCOPA-Sleep		X	Х
Sleep sub-study		X	Х
Stanford Sleepiness Scale (SSS)		X	
"Alertness Test"			
Depression short form		X	Х
Emotional and Behavioral		X	Х
dyscontrol short form			
Fatigue Severity Scale		X	Х
Pain Intensity 3a and Interference		X	Х
4a short forms			

 Table 5. Measurement tools performed in current study.

	1
Х	Х
X	Х
X	Х
X	Х
Х	Х
Х	Х
X	Х
X	
X	Х
X	Х
X	Х
	Х
	Х
	Х
X	Х
	Х
	X X X X X X X X X X

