#### C. Study Design and Research Methods C.1 Study design

The major purpose of this study is to assess the efficacy of CBD on motor symptoms of PD, and secondarily to study the safety and tolerability of CBD and other efficacy, particularly regarding tremor in PD. The study has been powered to detect a clinically significant reduction in MDS UPDRS Part III motor scores. This is a 1:1 parallel, double-blind, randomized controlled trial (RCT) with 60 participants. We will be recruiting up to 75 participants; the goal is to have 60 participants (30 in CBD group and 30 in placebo group) complete the study.

See Appendix 1 Schedule of Events for more detail on study design.

The study drug is obtained from NIDA. How the dose is started and escalated and what target dose is chosen is based on human literature and our open label study, as discussed in Section III under Discussion.

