#### C.2 Study Drug: CBD:

The study drug is supplied by NIDA; see Appendix 4 for Certificate of Analysis (COA). The study drug (CBD) is provided in the form of a thick liquid and will be diluted into a 100 mg/ml formulation with sesame oil. This procedure will be done by the PharmDs ([name], [name], and [name] as a consultant) or PI, according to the protocol we develop with guidance from NIDA and the University of Mississippi researchers that produced the material. The placebo will be made by the study Pharm Ds from USP grade sesame oil and food coloring. Because the placebo may be slightly different in appearance or taste, two study modifications are being done to preserve the blind. First, the study drug will be put into brown opaque bottles and the only study personnel to see the actual study drug will be the unblinded PharmD and the blinded CTRC PA that instructs the subject on how to take study drug. Further, the study drug is administered in a closed, vented room in the CTRC that removes the odor of cannabis within four minutes. After the study drug is administered and the study drug bottle closed, the PA will stay with the subject in the closed room while it is being vented for at least 10 minutes. The study design of parallel groups is being used instead of the original crossover design that was planned.

ElSohy Laboratories, Incorporated (ELI) will perform the stability testing. The laboratory is registered with the FDA and the DEA (Manufacturing and Analytical), all the planned analytical

procedures are validated, and the lab has extensive experience with the drug substance (CBD extract) and with a very similar drug product to ours. Controls for both CBD and THC content are used. The stability testing will be done in real time.

The shelf life will be determined by the testing described below. The final drug product will be stored at room temperature, 25°C.

The microbial testing for the final drug product will be carried out according to UPS 61 (total aerobic microbial count and total combined yeast/mold count) and USP 62 (for salmonella and E. coli), and the specification and acceptance criteria will be the same as recommended in USP <111> (microbiological examination of non-sterile products: Acceptance Criteria for Pharmaceutical Preparations and Substances for Pharmaceutical Use for non-sterile, non-aqueous products with oral administration). This will be the same for the product and placebo. Microbial Specifications:

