#### F. Data Analysis Plan:

Intention to treat concept is followed. In order to minimize data entry errors a double data entry system will be used.

If study participant agrees, the de-identified data would be shared within CDPHE Marijuana grantee consortium for future research.

The analysis will be performed in accordance with the analysis plan devised prior to unblinding. Baseline variables will be examined for equality between the two sequence groups. The primary, secondary and exploratory outcomes will be analyzed as below from baseline to the end of 2.5 mg/kg/day.

Primary Specific Aim: To evaluate the efficacy of CBD on motor symptoms in PD. The data will be analyzed to compare two randomized independent samples, CBD and placebo. Means and confidence intervals will be presented for the pre and post outcome values by treatment, and for the change scores between pre and post treatment within treatment group. A two independent sample T-test will compare the means of the change scores between the treatment groups. We will test the null hypothesis of no treatment effect. Longitudinal regression models will be fit for further analysis, including adjusting for covariates if necessary.

Secondary Specific Aim is to examine safety and tolerability of CBD and the effect of CBD on severity and duration of intractable tremor and other symptoms in PD.

Safety and tolerability and will be assessed in five ways:

- Frequency of study-related adverse events at each dose level collected at study visits. Analysis (frequency of study-related adverse events at each dose level in the two groups, treatment vs. placebo) will be mostly descriptive and proportions and confidence intervals will be calculated. Contrasts involving repeated measures on the same participants can be tested with McNemar's test (for two correlated proportions) or GEE models/GLMMs. Contrasts for independent data can be tested with standard two sample proportions test and with GLMs. Proportions, logistic regression, and relative risk regression can be applied to binary outcomes over a fixed period of time, and Poisson models can be applied to counts or events over time.

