- 2. Vital signs, orthostatic blood pressures, physical exam, EKG, and labs (hematology, complete metabolic profile, urinalysis) will be done during study visits. For vital signs and labs, data will be analyzed as a simple two-period trial. Means and confidence intervals will be presented pre and post treatment by treatment group, and for the change scores by treatment group. A two independent sample T-test will compare the means of the change scores between the treatment groups. More complex situations can be analyzed with longitudinal regression models.
- 3. Standardized assessment tools (MoCA, Cognition assessment battery, Anxiety short form, NPI, SCOPA-Sleep, ISI, DBAS-16, Pittsburgh Sleep Quality Index, RBDSQ, QUIP-RS, C-SSRS, Depression short form, Emotional Behavioral dyscontrol short form, Fatigue severity scale, MDS UPDRS, UDysRS, Pain Intensity 3a short form and Pain Intensity 4a short form, IRLS, PDQ-39 and EQ-5D-5L) and lab tests, the data will be analyzed as a simple two-period trial. Means and confidence intervals will be presented pre and post treatment by treatment group and for the change scores by treatment. A two independent sample T-test will compare the means of the change scores between the treatment groups. More complex situations can be analyzed with longitudinal regression models.
- 4. Proportion of participants who drop out of the study due to study drug intolerance. Analysis (proportions of participants who drop out of the study due to study drug intolerance in the two treatment groups) will be mostly descriptive, and proportions and confidence intervals will be calculated. Proportion differences between groups can be compared with the standard test.

**Exploratory Outcome Measures:** The efficacy of CBD on cognition, psychosis, sleep, daytime sleepiness, mood, fatigue, pain, impulsivity, other motor and non-motor PD signs, restless legs syndrome, REM sleep behavior disorder, quality of life, and plasma levels of cytokine are evaluated using the aforementioned assessment tools. The change from baseline to end of 2.5 mg/kg/day is compared.

Exploratory analyses: To study the efficacy of CBD on cognition, anxiety, psychosis, sleep, daytime sleepiness, mood, fatigue, pain, impulsivity, other motor and non-motor PD signs, restless legs syndrome, REM sleep behavior disorder, plasma levels of cytokine, and seborrheic dermatitis.

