Exploratory outcomes include assessments of cognition, anxiety, psychosis, sleep, daytime sleepiness, mood, fatigue, pain, impulsivity, other motor and non-motor PD signs, restless legs syndrome, REM sleep behavior disorder, and plasma levels of cytokine. Continuous outcomes will be analyzed in the same way as tremor. Transforms or non-parametric methods will be applied as necessary. Non-continuous outcomes will be analyzed with generalized estimating equations models, generalized mixed models, and McNemar's test for binary outcomes.

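### McNemar's test, listed for binary exploratory outcomes, can only measure change within one arm and cannot compare CBD with placebo in this parallel trial

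*Combined protocol and SAP*

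**What the plan says.** Section IV.C.1 sets the design: "This is a 1:1 parallel, double-blind, randomized controlled trial (RCT) with 60 participants". Section IV.C.2 adds that it replaced another one: "The study design of parallel groups is being used instead of the original crossover design that was planned".

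Section IV.A, under the exploratory outcome measures, sets the comparison of interest: "The change from baseline to the end of 2.5 mg/kg/day is compared between the two groups". Section IV.F treats the arms in the same way for the primary aim: "The data will be analyzed to compare two randomized independent samples, CBD and placebo".

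For exploratory outcomes that are not continuous, Section IV.F then lists generalized estimating equations, "generalized mixed models, and McNemar's test for binary outcomes". It gives no model terms, does not say which contrast each method serves, and names no test for independent proportions here.

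The adverse-event item of the same section is more careful. It confines the paired test to its proper use, "Contrasts involving repeated measures on the same participants can be tested with McNemar's test (for two correlated proportions) or GEE models/GLMMs", and separately names a two-sample proportions test and GLMs for independent data. Drop-outs due to intolerance also get a between-group comparison of proportions.

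**The concern.** McNemar's test compares two proportions measured on the same people and uses only the discordant pairs. In a crossover, each person supplies a CBD result and a placebo result, so the test can compare treatments. Here each person supplies results under one treatment only, so no CBD–placebo pair exists and the test cannot be formed for that contrast. What remains is baseline against follow-up inside one arm. That change mixes any drug effect with placebo response, regression to the mean and the passage of time.

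The named test therefore answers a different question from the one Section IV.A asks. If an analyst followed the sentence literally and reported a McNemar p-value for the CBD arm, the placebo arm would play no part in it. Section IV.F plans no multiplicity adjustment across outcomes, so nothing else in the plan would temper such a result.

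**Working it through.** **1. The plan's own figure, to show what is not affected.** The sample-size section uses a difference of 5.75 and an SD of 6.72: 5.75 / 6.72 = 0.856. A two-sided 5% independent-samples t-test (noncentral t) needs totals of 44.9 for 80% power and 59.4 for 90%, which become 46 and 60 with equal arms. Dividing by 1 − 0.20 gives 57.5, rounded up to 58, and 75. All four stated figures reproduce. They concern a continuous endpoint and a two-sample test, so McNemar's test does not enter them.

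**2. Which contrast each listed method can make in a parallel trial.**

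| Method listed for binary exploratory outcomes | Within-arm change | CBD versus placebo |
|---|---|---|
| McNemar's test | yes | no, there are no CBD–placebo pairs |
| GEE or generalized mixed model with a treatment term | yes | yes |

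**3. How far a within-arm McNemar result can mislead.** The documents give no rates for any binary outcome, so all rates below are assumptions. Both arms change equally, so there is no drug effect. The number of pairs is 30, the planned completers per arm in Section IV.C.1. The before/after correlation (phi) is taken as 0.3 or 0.5.

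With proportion p1 before and p2 after:
- P(yes, yes) = p1·p2 + phi·√[p1(1−p1)·p2(1−p2)]
- P(yes, no) = p1 − P(yes, yes)
- P(no, yes) = p2 − P(yes, yes)

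Example for 50% to 35% with phi 0.3: P(yes, yes) = 0.175 + 0.3 × √(0.25 × 0.2275) = 0.2465. The discordant cells are 0.50 − 0.2465 = 0.2535 and 0.35 − 0.2465 = 0.1035.

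Let b and c be the discordant counts. The exact version refers b to a binomial with b + c trials and probability ½. The asymptotic version rejects when (b − c)² / (b + c) > 3.84. Summing over all possible counts for 30 pairs gives these rejection probabilities:

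| Both arms | phi | Exact | Asymptotic |
|---|---|---|---|
| 50% to 35% | 0.3 | 18% | 26% |
| 50% to 35% | 0.5 | 23% | 35% |
| 50% to 30% | 0.3 | 34% | 43% |
| 50% to 30% | 0.5 | 44% | 59% |
| 15% to 10% | 0.3 | 2.3% | 9.6% |
| 15% to 10% | 0.5 | 1.5% | 9.8% |

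For comparison, a two-sample z-test of CBD against placebo at follow-up, with 30 per arm, rejects in 4.8%, 4.9% and 5.4% of trials when both arms stand at 35%, 30% and 10%.

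With 37 pairs (about half of the 75 to be recruited, with no drop-out) the first two scenarios rise to 24–42% and 44–69%.

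**The case against.** Four points on the other side have weight.

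**A valid route is already listed.** A reader who stops at McNemar's test might infer that the plan has no way to compare arms on a binary exploratory outcome. The documents do not support that. The same sentence lists GEE and generalized mixed models, and either compares the arms once a treatment term is included. What remains is narrower: no treatment term is stated, and nothing says which of the three methods decides.

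**Nothing says a within-arm result would count as efficacy.** A reader might infer that the trial will claim benefit from a McNemar p-value in the CBD arm. No section says so, Section IV.A requires a between-group comparison, and the adverse-event text shows that the authors know what the paired test is for. The risk is that the sentence permits this use, not that the plan intends it.

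**The harm is hypothetical.** The plan defines no specific binary exploratory endpoint. The tools in Section IV.A are mostly scored scales, and cytokines are levels. The pilot report also says participants had very little of most of these symptoms, which points towards the low-prevalence rows of the table. This stands, and it limits the weight of the point.

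**The crossover origin is not stated.** It is tempting to call McNemar's test a relic of the abandoned design. Section IV.C.2 and the mention of sequence groups in Section IV.F make that probable, but no section says it. Nor does the remark that "data will be analyzed as a simple two-period trial" show a wrong analysis: in both items where it appears, a two-independent-sample t-test on change scores follows.

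**Conclusion.** The point holds within limits. For binary exploratory outcomes the plan lists a test that cannot make the CBD–placebo comparison it calls for, and it omits both the within-participant restriction and the two-sample alternative that it gives for adverse events. That conclusion follows from the parallel design and needs no assumed rates.

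The practical size does depend on assumed rates. With no drug effect, 30 completers per arm and phi 0.3–0.5, a within-arm McNemar test is significant in 18–35% of trials for a fall from 50% to 35%, in 34–59% for a fall to 30%, and in about 1.5–10% for a fall from 15% to 10%. These are rates at which time or placebo change alone would produce a nominally significant result. They are not error rates of the trial's primary analysis.

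The primary t-test, the sample size, and the adverse-event and drop-out comparisons are sound on this point. It is a clarification worth making before unblinding, not a threat to the trial's main result.

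**What to change.** In the exploratory-outcomes paragraph of Section IV.F, replace McNemar's test for the treatment comparison with a between-arm analysis:

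- At the 2.5 mg/kg/day visit, use logistic regression of the binary outcome on treatment, adjusted for baseline status, and report the difference in proportions with a 95% CI.
- Where both dose visits are modelled, use GEE or a generalized mixed model with a treatment-by-visit term, and take the treatment contrast at the 2.5 mg/kg/day visit.
- For sparse outcomes, name a fallback such as Fisher's exact test. At 10% prevalence, 30 participants give about 3 events per arm, too few for a stable adjusted model.
- State which of these decides the comparison, and list the binary outcomes it applies to.

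McNemar's test may stay as a labelled descriptive summary of within-arm change, with no inference about CBD drawn from it. Removing the references to sequence groups and to a two-period trial is optional tidying that changes no analysis.

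The cost is a wording change. It needs no new data and leaves the sample size unchanged. Section IV.F already commits to an analysis plan devised before unblinding, so the change should be in place by then.

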#### Sample Size Justification

Using preliminary data we estimate a standard deviation for the within treatment UPDRS Motor change scores, post treatment compared to baseline, of 6.72, and a correlation between the paired observations of the change score of 0.75. Consistent with the preliminary data we anticipate a mean baseline UPDRS Motor score of 23, so a 25% treatment effect would have a magnitude of 5.75, less than the within treatment mean change score of magnitude 6.10 observed in the preliminary data. The estimated standardized effect size is 0.856. Therefore, the two independent samples T-test, testing for a between treatment difference on the within treatment UPDRS Motor change scores, at alpha = 0.05, would require a total sample size of 46 patients for 80% power, and 60 patients for 90% power. Compensating for the possibility of 20% drop out, we would need to recruit 58 patients for 80% power, and 75 patients for 90% power. Thus we plan to recruit 75 patients with a goal of having at least 60 patients complete the study.

Since other outcomes are either descriptive and/or exploratory, and sample size is limited, adjustment for multiple testing adjustments are not planned across different outcome variables.

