## Results

Figure 1 shows the trial profile. Data from all participants that took the study drug were analyzed for safety and tolerability, while only data from those that completed a final dose assessment were analyzed for efficacy. Table 1 shows the baseline clinical and demographic characteristics of safety and efficacy analysis groups.

Figure 1. Open label study profile

[figure not shown]

Table 1. Baseline demographics of the safety and efficacy analysis gro
--

	Safety analysis group (n=13)	Efficacy analysis group (n=10)
Age (years) (mean, SD)	68.1 (6.05)	68.7 (6.65)
Male (n, %)	10 (77%)	8 (80%)

Total MDS UPDRS score (mean, SD)	39.23 (13.32)	43.20 (12.21)
Motor MDS UPDRS score (mean, SD)	22.92 (9.30)	24.70 (8.93)
Disease duration, years (mean, SD)	6.08 (3.99)	6.30 (4.52)
Hoehn & Yahr Scale (mean, SD)	1.73 (0.56)	1.75 (0.59)
MoCA (mean, SD)	28.1 (1.63)	27.9 (1.60)
Levodopa Daily Dose Equivocation (LDDE) (mean, SD)	398.3 (331.00)	443.8 (348.97)

The demographics show that, in general, the participants had an age of onset consistent with the general population of persons with PD and they had early to early-middle stage PD. Generally they had mild bilateral motor symptoms, walked without assistance, had disease for six years, and required a relatively low dose of medication for their motor symptoms. An entry criteria required them to have a relatively significant tremor, but it would be a resting tremor and thus as a general group these participants likely had very little disability. These participants had scored in the normal range on the entry cognitive screening test.

The original protocol was that participants start at 5 mg/kg/day and titrate up to 25 mg/kg/day. Participants were to remain on each dose for three days, until the maximal tolerated dose was reached, and they were to be on that dose for 10-15 days, during which time they came in for an assessment visit.

Due to AEs experienced by our first five enrolled participants and the recommendations of the two PharmDs in our study, the protocol was changed to a slower titration and the maximal targeted dose was reduced from 25 to 20 mg/kg/day, since December 2016. There had been increased AEs and no evidence of additional benefit in the five participants beyond 20 mg/kg/day. Therefore, participants started at 5 mg/kg/day and increased every three to five days by 2.5 to 5 mg/kg/day until reaching a maximal targeted dose (20 mg/kg/day) or experiencing intolerable adverse effects.

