We considered other factors while choosing a study drug to use in the randomized controlled parallel study. While Epidiolex® was the best option for our open label dose-escalation study, we recognized that a disadvantage of using a pure CBD preparation and such a high dose is that it is different from what persons with PD obtain from local dispensaries. While local dispensaries sell cannabis that is

high in CBD, their products are not pure CBD and markedly lower doses are used, so our findings would not be very applicable to the products our PD patients are taking. The study drug and dosage to be used in the randomized controlled parallel study will be more similar to what persons with PD are obtaining from local dispensaries. Another consideration is that THC, CBD, and the other components of the cannabis plant interact, e.g., the "entourage" effect, and this interaction may have a meaningful effect, which would not be occurring in Epidiolex® since it is such a pure CBD product.

Therefore, we will use a cannabis extract with 59.3% CBD and 1.96% THC (30:1 CBD:THC) from NIDA. We will give 1.25 mg/kg twice daily of CBD and 0.041 mg/kg twice daily of THC. This equals 2.11 mg/kg twice daily (4.22 mg/kg/day) of the NIDA extract. For our average sized PD participant (84 kg) in our prior trial this will be approximately 100 mg CBD and 3.3 mg THC twice daily (morning and evening - > 6 hours apart). Therefore, the THC dose is below the threshold, ~5mg, that is expected to cause a person to feel "high." The interval of >6 hours is to minimize the possibility of the THC effect to overlap/build up. The extract solution will be in a sesame oil formulation, 100 mg/ml of CBD, so the participant would ingest 1 ml (100 mg CBD) twice daily. This much smaller amount of CBD and of oil is expected to be better tolerated, including less likely to cause liver enzyme elevations, than the study drug in the open label study.

In comparison to the open label study, the amount of CBD in this study is less than 15% (19.23/2.5). This dose and the fact that there is a small amount of THC is in the product makes this study drug more similar to what persons are receiving from local dispensaries, although it may generally have a higher in CBD content. Therefore, the results of the study using this product will be more generalizable to the Colorado PD population.

Whether participants should be allowed to drive has been carefully considered:

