# Inclusion and Exclusion criteria:

Inclusion criteria:

- Male or female participants 40 85 years of age.
- Willing and able to give informed consent (including through use of a legally authorized representative (LAR), if necessary).
- Idiopathic PD, per UK Parkinson's Disease Society (UKPDS) Brain Bank Clinical Diagnostic Criteria
- ON motor MDS UPDRS >20.
- Anti-parkinsonian medication is fixed for at least one month prior to the day the participant starts study drug treatment.
- If MoCA<22 participant must have a designated caregiver that agrees to ensure study protocols followed. This includes accompanying patient to study visits and being available for study phone calls.
- Must have a driver or available transportation (including provided Uber vouchers) to drive them to and from study visits and for other transportation needs during the treatment period.
- Has a significant other (someone who knows the participant well) that is appropriate for doing the NPI assessment, and agrees to do so
- Agrees to not take more than 1 gram per day of acetaminophen, due to a possible interaction with study drug that could increase risk of hepatotoxicity.

\*\*Note: the LAR (if required for informed consent), caregiver (required for those with MOCA<22), and significant other (required for all participants) may be the same person in some cases. In other cases, these may be different people.

Exclusion criteria:

- Known or suspected allergy to cannabinoids or excipients used in the study drug formulation.
- Cannabis is detectable at the screening visit by blood testing or at the baseline visit by urine testing. If cannabis is detected at either the screening or baseline visit, then the participant is a screen fail and may return >14 days later for a repeat screening visit. If cannabis is again detected at either the screening or baseline visit, then the participant is excluded and not allowed to rescreen.
- History of drug or alcohol dependence; defined by prior inpatient stay(s) for this or that patient states s/he has a history of this.
- Use of dopamine blockers within 180 days and cocaine, and MAO-A inhibitors within 90 days of baseline.

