On site screening visit: Consent, demographics, concomitant medications, family medical history, medical history and physical examination (complete physical exam and detailed neurological exam), vital signs, orthostatic blood pressures, tremor evaluation, MDS-UPDRS III, H&Y rating, MOCA, Drug, alcohol and tobacco abuse screening test, safety assessments (as listed in section IV A, including, QUIP-RS, C-SSRS, NPI, Emotional and behavioral dyscontrol short form, Drug abuse-related AEs), EKG and safety labs (including hematology, hemoglobin A1C, Complete metabolic profile and Liver Function Tests), blood cannabis analysis testing, plasma cytokine level tests, serum pregnancy test (for women childbearing potential), and inclusion/exclusion criteria are done. Study participants are instructed not to take cannabis from outside source throughout the study. Tremor constancy and amplitude measure device (Tremor GUI MATLAB package) is dispatched and participants are instructed to use the Tremor GUI MATLAB package to measure their tremors in the clinic and will perform it independently before they leave the clinic. They will measure the tremors at home twice a day (two hours after breakfast dose and two hours after dinner dose) for two days after screening visit and three days prior to the baseline visit.

To reduce in-person clinic visit time, part of the above procedures can be done remotely after onsite screening visit, including: demographics, concomitant medications, family medical history, medical history, safety assessments (C-SSRS, NPI, emotional and behavioral dyscontrol short form, drug abuse related AEs).

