Visit 2- Baseline visit: Eligibility confirmation (including tremor evaluation), medical history, concomitant medications collection, formal drug interaction assessment, vital signs, orthostatic blood pressures, brief physical exam, MoCA, MDS-UPDRS, H&Y rating, UDysRS, NMSS, OABSS, tremor constancy and amplitude two hours after taking study drug, TUG test, cognitive assessment battery (including tests of verbal intellectual function, attention, processing speed, executive function, verbal learning and memory, visuospatial memory, speeded verbal fluency, and word retrieval), Anxiety short form, Depression short form, SCOPA-Sleep, ISI, DBAS-16, Pittsburgh Sleep Quality Index, Alertness test, RBDSQ, C-SSRS, IRLS, Fatigue severity scale, Pain intensity and interference short form, PDQ-39, EQ-5D, CGI, PGI, urine drug (THC) test (urine dipstick test), urine pregnancy test (women childbearing potential) and study drug dispensing is done and, if appropriate, randomization. Skin evaluation (Dermatology Intake Form, DLQI, and dermatology

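### Does the entry floor of a motor score above 20 undermine the 25% effect behind the sample size?

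*Combined protocol and SAP*

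**What the plan says.** The Sample Size Justification (section F) takes a change-score SD of 6.72 and "a correlation between the paired observations of the change score of 0.75" from preliminary data. It sets the target with the words "we anticipate a mean baseline UPDRS Motor score of 23, so a 25% treatment effect would have a magnitude of 5.75", which gives a standardized effect of 0.856. For a two-sample t-test on change scores it derives 46 patients for 80% power and 60 for 90%, rising to 58 and 75 with 20% dropout.

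The inclusion criteria require "ON motor MDS UPDRS >20". The pilot in section III is described differently: "An entry criteria required them to have a relatively significant tremor", with no minimum motor score mentioned. Table 1 gives pilot baseline motor scores of 22.92 (SD 9.30) in all 13 patients and 24.70 (SD 8.93) in the 10 completers.

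Part III is scored at screening ("tremor evaluation, MDS-UPDRS III, H&Y rating, MOCA"). The full scale is repeated at Visit 2, which also includes "Eligibility confirmation (including tremor evaluation").

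**The concern.** A mean taken from a group that appears to have had no motor-score floor is carried into a trial that has one. Removing scores of 20 or below raises the mean. If the enrolled mean is well above 23, then 5.75 points is a smaller share of baseline than the stated 25%. A reader who takes the section as promising 90% power for a 25% reduction would then have the wrong denominator.

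The section also compares the target with a pilot change of 6.10. That is an uncontrolled change in 10 patients at a much higher dose; section III says "the amount of CBD in this study is less than 15% (19.23/2.5"). It is weak support for a between-arm difference of similar size.

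At stake would be the rationale for the target, and any later reading of the result as a percentage of baseline.

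**Working it through.** **The plan's own figures.** 0.25 × 23 = 5.75, and 5.75 / 6.72 = 0.856. A two-sided two-sample t-test at 0.05 (noncentral t) gives power of 81.0% with 23 per arm and 90.3% with 30 per arm. For dropout, 46 / 0.8 = 57.5, rounded up to 58, and 60 / 0.8 = 75. All stated figures reproduce.

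**Did the pilot include patients this trial would exclude?** Table 1 implies that 13 whole-number scores sum to 298 and the 10 completers' scores to 247, so the three non-completers sum to 51. With the two SDs as well, only four triples fit: {6, 22, 23}, {7, 18, 26}, {8, 16, 27} and {11, 12, 28}. Each contains a score of 20 or below. The lowest possible mean among pilot patients above 20 has only the score of 6 removed: (298 − 6) / 12 = 24.33. On that mean, 5.75 is 5.75 / 24.33 = 23.6%. This bound describes the 13 pilot patients and does not cover sampling error.

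**Size of the shift under a normal model.** The section's inputs imply a score SD of 6.72 / √(2 × (1 − 0.75)) = 9.50, taking equal SDs at both times. The share of a normal population with mean 23 scoring 20 or less is Φ((20.5 − 23) / 9.50) = 39.6%.

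The mean of those above the cut is m + s·φ(a)/(1 − Φ(a)), with a = (20.5 − m)/s. If eligibility rests on the screening score and the Visit 2 score partly regresses, the baseline mean is m + r × (truncated mean − m). The documents give no screening-to-baseline correlation, so r = 0.75 is an assumption; the column without regression is the other end of the range.

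| Source of m, s | Truncated mean | 5.75 as % | With r = 0.75 | 5.75 as % |
|---|---|---|---|---|
| Pilot, n = 13 (22.92, 9.30) | 28.9 | 19.9 | 27.4 | 21.0 |
| Pilot completers, n = 10 (24.70, 8.93) | 29.4 | 19.6 | 28.2 | 20.4 |
| Section F inputs (23, 9.50) | 29.1 | 19.8 | 27.5 | 20.9 |

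Gamma and lognormal shapes with the pilot means and SDs give 19.7 to 19.9% without regression. Varying the pilot mean (17.3 to 28.5), SD (6.7 to 15.4) and regression together stretches the range to 15.9 to 25.1%, so 25% is unlikely but not excluded.

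**Effect on power.** For 5.75 points at SD 6.72, power with 60 completers stays at 90.3%; the baseline mean does not enter the formula. For a true 25% effect at a baseline of 27.4 (0.25 × 27.4 = 6.85 points), power with 30 per arm depends on the change SD:

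| Change SD | Power for 6.85 points |
|---|---|
| 6.72 | 97.3% |
| 7.5 | 93.6% |
| 8.0 (6.72 × 27.4 / 23) | 90.3% |

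If the SD grows in proportion to the baseline, power for a 25% effect is what the plan states.

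**Where a percentage is used.** The primary outcome (section IV.A) is change in Part III. The Data Analysis Plan reports means, confidence intervals and a t-test on change scores. Section C.1 describes the power target as a clinically significant reduction and gives no percentage. The 25% appears only in deriving 5.75.

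**The case for a change.** The strongest case for a change is that the 25% is the only reason the section gives for choosing 5.75 points, and that the entry criterion makes it improbable. A mean of 23 with every score at least 21 leaves an average excess of only 2 points, so at most 2 / (30 − 21) = 22% of patients could score 30 or more. That sits badly with a pilot SD near 9. One sentence would correct it, and others may reuse the justification when designing later trials.

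The factual part stands: 23 was not adjusted for the floor. The need to act does not. Stating the target in points, which is the natural correction, repeats what the section already contains. To say that the criterion contradicts 25% goes too far, since the full range reaches 25.1%. A replacement percentage would also rest on 13 patients selected for tremor, with a mean Hoehn and Yahr stage of 1.73. This trial's inclusion list has no tremor criterion, and its randomization strata run to stage 5.

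On the pilot change of 6.10, the 95% interval is 6.10 ± 2.262 × 6.64 / √10, or 1.35 to 10.85. The section uses 6.10 only as a comparison. Section III already gives the n of 10, the dose difference and the caution that an open-label study cannot settle efficacy.

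**Conclusion.** The percentage label is probably loose, and nothing depends on it. If recruits resemble the pilot patients, 5.75 points is about 20 to 21% of the enrolled mean baseline. The sample size (46 and 60; 58 and 75 with dropout) and the 90% power for 5.75 points at SD 6.72 are correct and unaffected. The plan should not be called conservative for a 25% effect without a condition: power is about 97% at a change SD of 6.72, but falls to about 90% at 8.0. No outcome, test, enrolment figure or conclusion changes with the label, and the target in points is already on the page. A reader who wants a percentage can divide by the observed baseline mean, which the analysis plan already reports by arm. No change to the plan is needed.
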